6.3. Response Evaluation Criteria in Solid Tumors

Assessment of response and progression status in all subjects will be evaluated using the definitions from RECIST v1.1 for clinical decision-making and assessment of endpoints. Evaluation for target, non-target, and new lesions based on RECIST v1.1 are to be considered.

For a best overall response of CR or PR, confirmation of the response is required at a subsequent timepoint at least 4 weeks after the initial observation. Confirmed CR or PR will be claimed only if the criteria for each are met at that subsequent timepoint as outlined in [Appendix 7](#).

Table 2 Evaluation of Best Overall Response When Confirmation of CR and PR Required

Overall Response		Best Overall Response at that Time Point
First Time Point	Second Time Point	
CR	CR	CR
CR	PR	SD, PD, or PR ^a
CR	SD	SD provided minimum criteria for SD duration met ^b , otherwise, PD
CR	PD	SD provided minimum criteria for SD duration met ^b , otherwise, PD
CR	NE	SD provided minimum criteria for SD duration met ^b , otherwise, PD
PR	CR	PR
PR	PR	PR
PR	SD	SD
PR	PD	SD provided minimum criteria for SD duration met ^b , otherwise, PD
PR	NE	SD provided minimum criteria for SD duration met ^b , otherwise, PD

Abbreviations: CR = complete response; NE = not evaluable; PD = progressive disease; PR = partial response; SD = stable disease.

^a If a CR is truly met at the first timepoint, then any disease seen at a subsequent timepoint, even disease meeting PR criteria relative to baseline, makes the disease PD at that point (since disease must have reappeared after CR). Best response would depend on whether minimum duration for SD was met. However, CR may be claimed when subsequent scans suggest small lesions were likely still present and in fact the subject had PR, not CR at the first timepoint. Under these circumstances, the original CR should be changed to PR and the best response is PR.

^b Minimum required duration of SD is 6 weeks.

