9.3.1. Efficacy Analyses

Efficacy analyses will be performed separately for each cohort. RECIST 1.1 criteria will be used for the primary endpoint evaluation ([Eisenhauer et al., 2009](#)), and iRECIST will be used for the exploratory endpoint response evaluation ([Seymour et al., 2017](#)). The iRECIST endpoints are analyzed using the same statistical methodology and the results will be presented in the same ways for the corresponding RECIST 1.1 endpoints.

The primary efficacy endpoint is the ORR defined as the proportion of subjects who achieve confirmed CR or PR per RECIST v1.1. The best overall response is the best response recorded from the start of the treatment until PD. The smallest measurements recorded since the treatment started will be used as the reference for PD. Subjects with CR or PR are considered to have obtained objective response. Subjects with not-evaluable response (NE) are counted as non-responders. Exact 95% CI will be constructed for the ORR for each cohort.

Subjects with CR, PR or SD are considered to have achieved disease control. Disease control rate is defined as the proportion of subjects who have achieved CR, PR, and SD. Duration of response only applies to subjects whose best overall response is CR or PR and is defined as the number of days from the first documentation of objective tumor response to the date of first PD or death due to underlying cancer.

Duration of stable disease is measured from the start of the treatment (the first treatment date for non-randomized studies, the randomization date for randomized studies) until the date when the criteria for overall disease progression are first met.

Duration of response is the time from first evaluation showing CR or PR (response confirmation required at subsequent tumor assessment no earlier than 4 weeks after first evaluation showing CR or PR) to the time of the first subsequent evaluation showing PD or death. Only subjects who experience a confirmed CR or PR will be analyzed for DoR. Subjects who do not experience PD or death will be censored per the censoring rules in the statistical analysis plan.

Progression-free survival is defined as the number of days from Day 1 in Cycle 1 to the first documented progression or death due to any cause. Only deaths that occurred within 30 days of the last progression assessed.

Overall survival is defined as the time from the first dose of study drug to death due to any cause.

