- Tumor markers alone cannot be used to assess response. If markers are initially above the upper normal limit, they must normalize for a subject to be considered in complete response when all lesions have disappeared.
- Cytology and histology can be used to differentiate between PR and CR in rare cases (eg, after treatment to differentiate between residual benign lesions and residual malignant lesions in tumor types such as germ cell tumors).

Baseline Documentation of “Target” and “Non-Target” Lesions

- All measurable lesions up to a maximum of two lesions per organ and 5 lesions in total, representative of all involved organs should be identified as **target lesions** and recorded and measured at baseline.
- Target lesions should be selected on the basis of their size (lesions with the longest diameter [LD]) and be representative of all involved organs, but in addition should lend themselves accurate repeated measurements.
- A sum of the LD for all target lesions will be calculated and reported as the baseline sum diameters. The baseline sum diameters will be used as reference by which to characterize the objective tumor. If lymph nodes are to be included in the sum, then as noted above, only the short axis is added to the sum.
- If a target lesion becomes too small to measure, a default value of 5 mm is assigned. If the lesion disappears, the measurement is recorded at 0 mm.
- If extranodal target lesions fragment, the LDs of the fragmented portions are added in the sum. If targets lesions coalesce and cannot be distinguished, the LD of the coalesced lesion is added to the sum.
- For a subject with SD or PR, a lesion which disappears and then reappears will continue to be measured and added to the sum. Response will depend upon the status of the other lesions. For a subject with CR, reappearance of a lesion is considered PD.
- New lesions should be unequivocal and not attributable to differences in scanning technique or findings which may not be tumor. If a new lesion is equivocal, repeat scans are needed to confirm. If confirmed, PD is assessed from the date of the first scan.
- All other lesions (or sites of disease) should be identified as **non-target lesions** and should also be recorded at baseline. Measurements of these lesions are not required, but the presence or absence of each or in rare case unequivocal progression should be noted at each subsequent response assessment.

RESPONSE CRITERIA

Evaluation of Target Lesions

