For either CR or PR to be ‘confirmed’ the same overall response needs to be achieved at the subsequent visit, which should be at least 4 weeks later. The best overall response (BOR) is then the best response achieved in order of CR, PR, SD, PD, NE, where a subject cannot be defined as having BOR of CR, PR or SD if they have previously experienced PD.

Response is recorded for each participant at each tumor response visit using the criteria outlined above. The response recorded in the database will be used to evaluate the objective response rate and all other endpoints related to the response based on RECIST v1.1 guidelines.

Objective Response Rate (ORR) is then defined as the proportion of subjects who achieve a best overall response of Confirmed CR or Confirmed PR. Subjects with not-evaluable response (NE) are counted as non-responders.

The number and percentage of subjects who have achieved objective response will be summarised, by cohort, including sub-cohort, along with the 95% Clopper-Pearson CI.

Additionally the number and percentage of subjects with CR and PR (confirmed and unconfirmed), SD, PD and NE will be summarised by cohort, including sub-cohort.

A swimmer plot, displaying the response for each subject over their time in the study, will be presented for all subjects as well as for gynaecological cohorts (Cohort A, E and H) and rare tumor sub-cohorts (Cohort F) with a line per subject and each response/important event highlighted on the line as appropriate.

A waterfall plot will also display the percentage reduction in overall sum of diameters over the time in study for each subject. This will again be presented for all subjects and for gynaecological cohorts

(Cohort A, E and H) and rare tumor sub-cohorts (Cohort F). Additionally a spider plot will be produced for each set of cohorts, which will display the percentage change from baseline in sum of the longest diameter over time, where the lines will be displayed by best overall response.

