10.8.2.2. Duration of Response

Duration of response (DoR) is defined as the time, in days, from the first of the 2 assessments required for confirmed PR or CR to the time of the PD or death due to underlying cancer.

The duration will be calculated (in days) as:

Date of first overall response of PD or date of death due to underlying cancer (whichever is first) – Date of first of the two assessments required for confirmed CR or PR.

The duration of response will be summarised by cohort using descriptive summaries, which will not account for censoring. Additionally, Kaplan-Meier curves will be produced for each cohort along with a table summarising the median and 25th and 75th percentiles of the duration of response, inclusive of censoring, for each cohort, including sub-cohort.

[Kaplan-Meier plot: y-axis = cumulative proportion of participants who still have response, x-axis = day, one line for each cohort, including sub-cohort, overlayed on the same plot].

Exclusion

If a subject does not achieve confirmed CR or PR they will be excluded from this analysis.

Censoring

If a subject does not experience PD or death due to underlying cancer their duration will be censored at the date of their last disease assessment.

If a subject dies due to a cause other than underlying cancer they will be censored at the date of death.

If a subject does not have a disease assessment after their assessment confirming their response as CR or PR they will be censored at the date of their last disease assessment.

If a subject initiates another cancer treatment prior to PD/death their duration of response will be censored at the last assessment prior to initiation of the alternative cancer treatment.

If a subject experiences PD or death immediately following 2 or more visits at which their response was missing or NE their duration of response will be censored at the time of their last assessment prior to missing/NE response.

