As with RECIST v1.1, iRECIST defines confirmed iCR and iPR response as the same overall response being achieved at the subsequent visit, which should be at least 4 weeks later. The best overall

response is then the best response achieved in order of iCR, iPR, iSD, iUPD, iCPD, NE. A subject can experience iUPD prior to any response, but not iCPD.

Immune Objective Response Rate (iORR) is then defined as the proportion of subjects who achieve a best overall response of iCR or iPR (confirmed). Subjects with not-evaluable response (NE) are counted as non-responders.

The number and percentage of subjects who have achieved objective response will be summarised, by cohort, including sub-cohort, along with the 95% Clopper-Pearson CI.

Additionally the number and percentage of subjects with iCR and iPR (confirmed and unconfirmed), iSD, iUPD, iCPD and NE will be summarised by cohort, including sub-cohort.

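### The SAP lets only a second PR confirm a PR, so a protocol responder with PR then an unrepeated CR drops out of ORR and DoR, and section 11 does not declare the change

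*SAP*

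**What the plan says.** **SAP.** Section 10.8.1.1 sets one condition for confirming either type of response: "the same overall response needs to be achieved at the subsequent visit, which should be at least 4 weeks later". ORR then counts only a best overall response of confirmed CR or confirmed PR. For DoR, section 10.8.2.2 states that "If a subject does not achieve confirmed CR or PR they will be excluded from this analysis", and the clock starts at the "Date of first of the two assessments required for confirmed CR or PR". The iRECIST sections repeat the approach: section 10.8.3.1 says that "iRECIST defines confirmed iCR and iPR response as the same overall response being achieved at the subsequent visit", and section 10.8.3.2 carries over the DoR start date and exclusion.

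**Protocol.** Section 6.3 requires confirmation at least 4 weeks after the first observation and gives a table for that case, Table 2, "Evaluation of Best Overall Response When Confirmation of CR and PR Required". Its row for PR at the first time point and CR at the second gives PR, with no condition that the CR be repeated. Footnote a covers the reverse order: if a CR was truly met, "any disease seen at a subsequent timepoint, even disease meeting PR criteria relative to baseline, makes the disease PD at that point". Appendix 7 agrees: "For a subject with CR, reappearance of a lesion is considered PD". On DoR, section 9.3.1 says that "Duration of response is the time from first evaluation showing CR or PR". The Appendix 7 comparison of RECIST 1.1 with iRECIST takes confirmation of CR and PR in iRECIST to be the same as in RECIST 1.1.

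**Declaring changes.** SAP section 4 says departures from the protocol's analyses will be listed in section 11. Section 11 has two items: an added TEAE definition and the omission of summaries of laboratory toxicity grades.

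**The concern.** A patient whose tumor goes from PR to CR has improved, and Table 2 credits that patient with at least a PR. Under the SAP sentence the same patient has no confirmed response unless the CR is repeated or an earlier pair of PRs exists. This rule derives the primary endpoint, so the two documents define ORR differently. The cohorts are small, and one reclassified subject visibly changes the reported rate, its confidence interval and the set analysed for DoR. If the stricter rule is deliberate, it is a change to the primary analysis that the SAP's own section 4 says should be declared.

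**Working it through.** **Design figures.** The plan gives no figure for this rule. Its ORR design figures can be reproduced as the sum, over x1 at or above the stage 1 cut, of P(Bin(10, p) = x1) × P(Bin(19, p) ≥ r − x1), where r is the total number of responders required.

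- Type 1 (cut 1, r = 4): 0.0468 at p = 0.05 and 80.11% at p = 0.2, as stated.
- Type 2 (cut 2, r = 6): 0.0471 at p = 0.1 and 80.51% at p = 0.3, as stated.

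The confirmation wording does not change these figures. SAP 10.1.3 plans no hypothesis test, so the effect is worked out on the reported estimates.

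**Step 1: classify visit sequences.** The SAP rule needs adjacent PR-PR or CR-CR before any PD. Table 2 accepts those and adjacent PR-CR, subject to footnote a. Visits are taken to be at least 4 weeks apart.

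| Sequence | SAP 10.8.1.1 | Protocol Table 2 |
|---|---|---|
| PR, CR (last scan) | not a responder | responder (PR) |
| PR, CR, then NE, SD or PD | not a responder | responder (PR) |
| PR, PR, CR | responder | responder |
| PR, CR, CR | responder | responder |
| CR, PR, PR, with the CR true | responder | not a responder |
| CR, PR, PR, with the CR re-read as PR | responder | responder |

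The first two rows are the main conflict. The fifth runs the other way and arises only if a true CR is followed by visits recorded as PR.

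**Step 2: effect on ORR.** Losing one responder lowers ORR by 100/n percentage points. The Clopper-Pearson limits for x responders of n are the 0.025 quantile of Beta(x, n − x + 1), taken as 0 when x = 0, and the 0.975 quantile of Beta(x + 1, n − x). Final cohort sizes are not given, so n is an assumption: 10 is the Simon stage 1 size, and 20 is the per-cohort maximum in SAP 6.1.

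| Assumed n | Table 2 | SAP rule, one PR-then-CR subject lost |
|---|---|---|
| 10 | 2/10 = 20.0% (2.5 to 55.6) | 1/10 = 10.0% (0.3 to 44.5) |
| 10 | 1/10 = 10.0% (0.3 to 44.5) | 0/10 = 0.0% (0.0 to 30.8) |
| 20 | 2/20 = 10.0% (1.2 to 31.7) | 1/20 = 5.0% (0.1 to 24.9) |

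**Step 3: effect on DoR.** A PR-then-CR subject with no repeat is excluded. For PR, CR, CR the two assessments that confirm under the SAP are the CRs, so the SAP starts at the first CR and protocol 9.3.1 at the PR. Take PR at week 8, CR at weeks 16 and 24, and PD at week 40:

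- Protocol: (40 − 8) × 7 = 224 days.
- SAP: (40 − 16) × 7 = 168 days.
- Difference: 56 days, one 8-week scan interval.

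If both scans use the ±1 week window, the interval is (8 ± 2) × 7 = 42 to 70 days. On a 12-week schedule after Week 48 it is nominally 84 days.

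**Step 4: declaration.** Neither item in SAP section 11 concerns confirmation, best overall response or the DoR start.

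**The case against.** The best defence is that the sentence is shorthand. A CR normally also meets the PR criterion of at least a 30% decrease, the SAP says its endpoints follow RECIST v1.1, and it presents itself as a more detailed account of the protocol's analyses. On that reading nothing has changed and section 11 needs no entry. This may well be the intention, but the text does not say it. SAP Table 5 assigns CR and PR as separate overall responses, so a programmer following the sentence would code PR-PR or CR-CR.

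Other points have more force:

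- **DoR start.** This follows from the confirmation rule. Once a CR can confirm a PR, the existing wording can be read as starting at the PR. The day counts also assume scans on schedule, whereas unscheduled scans are used for efficacy.
- **Footnote a.** If investigators follow Appendix 7, a reappearing lesion after a true CR is recorded as PD, and SAP 10.8.1.1 bars any response after PD. The CR, PR, PR discrepancy is therefore remote, though Table 2 does provide for a CR then PR record.
- **Consequence.** The study was terminated, no test is planned and the iRECIST limb is exploratory. The shell for Table 14.2.1 has separate rows for unconfirmed CR and PR, and visit responses are listed, so an affected subject could be traced. The ORR row would still leave that subject out.

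**Conclusion.** The concern holds. As written, SAP 10.8.1.1 contradicts the PR-then-CR row of protocol Table 2 for the primary endpoint, and the difference is not declared. Each affected subject lowers a cohort's ORR by 100/n percentage points (10 at n = 10, 5 at n = 20) and leaves the DoR analysis. For PR, CR, CR only DoR changes, by one scan interval. For the PR-then-CR pattern the SAP can only lower ORR. Because footnote a is also missing, the overall direction is not strictly one-way.

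The conclusion rests on a literal reading of the SAP sentence and the illustrations on assumed cohort sizes. The documents do not say how many subjects show the pattern, and the number may be zero. It should be fixed because it concerns the rule that defines a responder, but it does not undermine the design.

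**What to change.** - **SAP 10.8.1.1:** state that a PR is confirmed by a PR or CR, and a CR by a CR, at a subsequent assessment at least 4 weeks later, and that best overall response is assigned by protocol Table 2 with its footnotes. Footnote a covers disease after a true CR. Footnote b, the 6-week minimum for SD, bears on SD and DCR rather than ORR and is cited only so that the whole table applies.
- **SAP 10.8.3.1:** use the same PR-or-CR confirmation wording for iRECIST.
- **SAP 10.8.2.2 and 10.8.3.2:** start DoR at the first CR or PR of the confirmed response, so that for PR, CR, CR it starts at the PR.
- **If the stricter rule is intended:** keep it, and list and justify it in section 11.

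The cost is one sentence in each of four SAP sections and a programming check before database lock. No new data are needed.

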1.4.2. Scientific Rationale for Selected Endpoints

In oncology clinical trials, many different endpoints can be used as primary or secondary endpoints including OS, ORR, DoR, disease control rate (DCR), disease-free survival (DFS), and PFS.

The ORR, as per RECIST v1.1, is an increasingly important endpoint for accelerated development of highly active anticancer therapies and will be the primary endpoint for this study. This surrogate marker, used in single arm studies, is able to evaluate early if there is a direct effect on tumor size seen on radiology. The ORR has correlated with endpoints such as PFS and OS.

As per Food and Drug Administration (FDA) guidance document on oncology endpoints, ORR was chosen because:

- ORR is generally assessed earlier and with smaller sample size compared with survival studies.
- ORR measures the effect on tumor attributable to drug(s), not natural history.
- ORR is generally based on objective and quantitative assessment.

Additional secondary and exploratory endpoints that will also be evaluated include the following:

The DoR is defined as the time from first documented objective response (RECIST v1.1) by Independent Central Review until the date of documented disease progression. Cancer drugs that demonstrate improved DoR can produce a durable, meaningful delay in disease progression, as opposed to a temporary response without any lasting benefit. The DCR, as per RECIST v1.1 is a modification of ORR that includes subjects with SD exceeding a minimum duration as responders. This may be a suitable preliminary or exploratory measure of antitumor activity for indications where complete response (CR) or partial responses (PR) may be more difficult to attain, stable disease does not reflect the natural history of the disease, and SD is a clinically meaningful outcome. Duration of stable disease is measured from the start of the treatment (the first treatment date for non-randomized studies, the randomization date for randomized studies) until the date when the criteria for overall disease progression are first met also provides supportive data for assessment of clinical activity of experimental anti-cancer regimens.

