- Screening and subsequent tumor assessments must include CT scans (with IV contrast unless contraindicated and oral contrast as appropriate per institutional standards) of the chest, abdomen, and pelvis. If a CT scan for tumor assessment is performed in a positron emission tomography (PET)/CT scanner, the CT acquisition must be consistent with the standards for a full-contrast CT scan. Brain imaging (either MRI or contrast-enhanced CT) is required at screening for all subjects. Further investigations such as bone scans and CT scans of the neck should also be performed if there is any clinical suspicion of disease at any site that may not be demonstrated by the minimum schedule of assessments listed above. At the investigator's discretion, other methods of assessment of measurable disease as per RECIST v1.1 may be used. The same radiographic procedures used to assess disease sites at screening should be used throughout the study (eg, the same contrast protocol for CT scans). Response will be assessed by the investigator on the basis of physical examinations and the imaging modalities detailed above, using RECIST criteria. Assessments should be performed by the same evaluator if possible to ensure internal consistency across visits.

Tumor assessments will be performed every 8 weeks (± 1) from Cycle 1 Day 1 or as clinically indicated through to week 48 and then at least every 12 (± 1) weeks. Response assessment data (i.e., progressive disease or no progression of disease) will continue to be collected (based on standard-of-care radiographs) for subjects who have not progressed at the time of the termination visit, until the subject starts alternative anti-cancer treatment or develops progressive disease, whichever occurs first. Response assessment and assessment of tumor markers will be obtained at treatment termination, unless a prior radiographic assessment has been performed within the last 14 days or at a prior response assessment that documented progressive disease. At the investigator's discretion, scans may be performed at any time if progressive disease is suspected.

- d. Concomitant medications include any prescription medications or over-the-counter medications. At subsequent visits, changes to current medications, or medications used since the last documentation of medications will be recorded.

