10.1. Statistical Considerations

10.1.1. General Definitions

In all applicable summary/analysis presentations of safety endpoints, Baseline is defined as the last non-missing assessment value for a subject, for that particular parameter, that is prior to dosing with study drug on Day 1 (including unscheduled assessments), unless over-ruled after review of data at the DRM or otherwise stated in the appropriate endpoint sections below. Study drug includes both etigilimab and nivolumab.

For efficacy endpoints, the baseline definition is as per the appropriate endpoint sections below. For the derivation of most efficacy endpoints, the first post-baseline assessment to be used should be the first assessment that was taken after the first dose of study drug.

Within summary presentations/analyses by visit it is envisaged that only scheduled protocol visit values will be used for post-baseline time points. In the clinical database a number of data points have been labelled as unscheduled/additional recordings of data. These data points will generally be included within subject listings only. However, at the DRM the occurrence of such unscheduled data will be reviewed for each subject to decide if (and how) any such data point(s) should be included within summary presentations/analyses. Any such decisions will be documented in the DRM minutes.

Efficacy endpoints will be determined using all available data, including unscheduled visits.

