10.8.2. Secondary Endpoints

10.8.2.1. Disease Control Rate

Disease control rate (DCR) is defined as the proportion of subjects who have achieved CR, PR, and SD. The number and percentage of subjects who have achieved disease control will be summarised, by cohort, including sub-cohort, along with the 95% Clopper-Pearson CI.

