95% CI	XX.X, XX.X	XX.X, XX.X	XX.X, XX.X	XX.X, XX.X	XX.X, XX.X	XX.X, XX.X	XX.X, XX.X	XX.X, XX.X	XX.X, XX.X	XX.X, XX.X

Response as per RECIST v1.1: CR = Complete Response, PR = Partial Response, SD = Stable Disease, PD = Progressive Disease.

De-Diff LPS = Dedifferentiated Liposarcoma, UPS = Undifferentiated pleomorphic sarcoma, GCT = Germ Cell Tumors.

[1] 1 SD includes Stable Disease following one scan. 2 SD includes Stable Disease following 2 or more scans.

Note: Objective Response Rate is calculated as the number of subjects with a confirmed complete response or partial response divided by the number of subjects in the analysis set.

Note: Disease Control Rate is calculated as the number of subjects with a confirmed complete response, partial response or stable disease divided by the number of subjects in the analysis set.

Note: No subjects were recruited into Cohort D and so this cohort is not displayed.

Note: No subjects in Cohort B are in the Response-Evaluable Analysis Set and so this cohort is not displayed here.

Source: Listing 16.2.6.4.1

This table shell will be used for

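### The SAP counts any stable disease in DCR without the protocol's 6-week minimum, so SD seen only on an early termination or unscheduled scan can count as disease control

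*SAP*

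**What the plan says.** **Protocol, with a minimum.** Section 6.3, Table 2, note b: "Minimum required duration of SD is 6 weeks". Most of the unconfirmed CR and PR rows of that table give "SD provided minimum criteria for SD duration met", and PD otherwise. Section 1.4.2 describes DCR as a modification of ORR that "includes subjects with SD exceeding a minimum duration as responders".

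**Protocol, without a minimum.** The endpoint table in section 2, section 9.3.1 and the synopsis define DCR from CR, PR and SD and state no duration.

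**SAP.** Section 10.8.1.1: "The best overall response (BOR) is then the best response achieved in order of CR, PR, SD, PD, NE". The only restriction added is that CR, PR or SD cannot follow an earlier PD. Section 10.8.2.1: "Disease control rate (DCR) is defined as the proportion of subjects who have achieved CR, PR, and SD". Section 10.1.1: "Efficacy endpoints will be determined using all available data, including unscheduled visits". The Table 14.2.1 shell splits SD by number of scans, not by time: "1 SD includes Stable Disease following one scan". The same shell serves Table 14.2.4 for iRECIST.

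**Early scans.** Protocol 8.1, note c: "Response assessment and assessment of tumor markers will be obtained at treatment termination", unless a scan was done in the previous 14 days or PD is already documented. The same note allows scans at any time when progression is suspected.

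SAP section 4 says deviations from the protocol-specified analyses are listed in section 11. Section 11 covers an added TEAE definition and the unsummarised laboratory toxicity grades. It does not mention the SD minimum.

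**The concern.** A minimum duration for SD exists so that an unchanged tumour counts as benefit only after it has had time to grow. A programmer following SAP 10.8.1.1 and 10.8.2.1 as written would apply no such check. SD read a few weeks after first dose then becomes a best overall response of SD and enters the DCR numerator.

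The same scan can bring the subject into the Response-Evaluable set, since one post-baseline assessment is enough (SAP section 9). DCR is a secondary efficacy endpoint reported by cohort and sub-cohort, so a single subject can move it visibly. The error runs in one direction only: it can raise DCR but not lower it.

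**Working it through.** The documents state no DCR figure, so there is none to reproduce. Times below are elapsed days from first dose, as in the SAP's duration formulas.

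**1. Which scans can fall short of the minimum?**
- Minimum: 6 × 7 = 42 days.
- Earliest scheduled scan: 8 − 1 = 7 weeks = 49 days (protocol 6.1, 8.2). This exceeds 42, so scheduled scans cannot cause the problem.
- Termination scan: the termination visit falls within 30 days of the last dose (protocol section 7). A subject who receives only Cycle 1 has a last dose on Study Day 3 (nivolumab), so the visit is due by Study Day 3 + 30 = 33, which is 32 elapsed days. This is below 42.
- Unscheduled scan: no earliest date is set.

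**2. What happens after an early SD?**

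| Early SD (before 42 days), then | SAP as written | Protocol minimum |
|---|---|---|
| SD on a scan at or after 42 days | disease control | met; no difference |
| PD before 42 days | disease control | not met |
| no later evaluable scan | disease control | not met |
| PD at Week 8 | disease control | depends on how SD is dated |

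In the last row, protocol 1.4.2 and 9.3.1 measure duration of SD from start of treatment to PD. That gives 8 × 7 = 56 days, and the minimum is met. If SD must instead be documented on a scan at or after 42 days, it is not met. Neither document says which applies to best overall response. The second and third rows are therefore the clear cases.

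**3. Size.** With k such subjects in a cohort of n, DCR is raised by k/n. For k = 1: 1/10 = 10.0 points, 1/20 = 5.0 points, 1/29 = 3.4 points.

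Illustration, assuming a DCR near 50% under the SAP rule (k and the starting DCR are both assumed):

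| n | SAP DCR | k | DCR with minimum (Clopper-Pearson 95% CI) |
|---|---|---|---|
| 10 | 5/10 = 50.0% | 1 | 4/10 = 40.0% (12.2–73.8) |
| 10 | 5/10 = 50.0% | 2 | 3/10 = 30.0% (6.7–65.2) |
| 29 | 15/29 = 51.7% | 1 | 14/29 = 48.3% (29.4–67.5) |
| 29 | 15/29 = 51.7% | 3 | 12/29 = 41.4% (23.5–61.1) |

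With k = 0 nothing changes.

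**4. What is not affected.** ORR requires confirmed CR or PR, and the Simon rules count responders, so neither depends on how SD is classified.

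**The case against.** The strongest reply is that the SAP has dropped nothing. SAP 10.8.2.1 follows the DCR definition in protocol 9.3.1 closely, and neither that section, the endpoint table nor the synopsis carries a minimum. Note b belongs to a table about confirming CR and PR: no row starts with SD, and the marker sits only on unconfirmed CR/PR rows. Section 1.4.2 is rationale text and gives no number. Much of this stands. A reader might infer that the SAP alone removed a settled protocol rule, but the inconsistency starts inside the protocol. Still, note b is worded generally. Confining it to its rows would require 6 weeks of an early PR that then progresses, and nothing of a plain SD at the same visit.

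Second, a reader might infer that anyone who stops early with an SD scan is miscounted. That is not so. Protocol 4.2 and 6.1 keep subjects who stop before confirmed progression on the planned scans, and an SD at Week 8 satisfies the minimum. Nor is early SD followed by PD at Week 8 a clear error, for the reason shown in step 2.

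Third, the effect may be nil. Assuming that 5–15% of subjects are affected and concluding that DCR is 5–15 points too high only restates the assumption; the documents give no such frequency.

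Fourth, the outputs offer some visibility: the response table separates SD on one scan from SD on two or more, duration of stable disease is listed beside best response, and swimmer plots show timing. A careful reader could find early-only SD there, but the reported DCR would still include it.

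A reference to RECIST v1.1 in SAP 10.8.1.1 does not close the gap, because the section states its own ranking and uses the recorded visit responses.

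**Conclusion.** The point holds as a gap between documents with a conditional effect. The protocol states a 6-week minimum for SD in one place and omits it from its DCR definitions; the SAP applies no minimum and does not address the discrepancy. Followed as written, the SAP counts as disease-controlled a subject whose only non-PD evidence is a termination or unscheduled scan before 42 days and who then has PD before 42 days or no later evaluable scan.

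Each such subject adds 1/n to DCR: 3.4 points at n = 29, 10 points at n = 10. The number of such subjects is not given and may be zero, so the documents do not support a statement that DCR is inflated by any particular amount. The conclusion rests on reading note b as applying to SD generally, which is the natural reading of its words but still a reading. DCR is descriptive and no hypothesis test is planned (SAP 10.1.3). It is worth correcting because the remedy is simple and the error favours the treatment.

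**What to change.** - In SAP 10.8.1.1 and 10.8.2.1, state that a best overall response of SD (and of iSD, in 10.8.3.1) requires the protocol's 6-week minimum from first dose.
- State how the minimum is dated: either SD documented on a scan at or after 42 days, or time from first dose to PD. This settles early SD followed by PD at Week 8.
- State that SD short of the minimum does not count in DCR. Classify it as PD if the next assessment is PD, and as NE if there is no later assessment. For unconfirmed CR or PR, follow protocol Table 2, which gives PD when the minimum is not met, including when the next time point is NE. The choice between PD and NE does not alter DCR.
- Footnote the rule in Tables 14.2.1 and 14.2.4.
- Align the DCR wording in protocol 9.3.1, or record the clarification in SAP section 11.

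The cost is a few sentences in the SAP and one date check in the best-response derivation, on data already collected. The downside is that DCR may come out slightly lower.
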